##### 5.1.1.2 Secondary efficacy parameters

The following criteria were selected as secondary efficacy criteria of the therapy in all study groups for a comparative assessment of the therapeutic effect:

- The occurrence of bowel movements per day (according to the diary data) in the treatment group compared with the placebo group;
- The incidence of any diarrhea in the treatment group compared with the placebo group;
- The incidence of C. difficile-associated AAD in the treatment group compared with the placebo group;
- The incidence of AAD not associated with C. difficile in the treatment group compared with the placebo group;
- The duration of AAD (the time from the onset of AAD to the normalization of stool form according to BSFS (types 1, 2, 3 and 4) and the presence of normal stool within 48 hours)) in the treatment group as compared to the placebo group;

- Duration of any diarrhea (the period from the diarrhea onset to the normalization of stool form according to BSFS (types 1, 2, 3 and 4) and the presence of normal stool within 48 hours)) in the treatment group vs the placebo group;
- The changes in stool consistency (according to Bristol Stool Form Scale) (according to the diary data) in the treatment group as compared to the placebo group;
- The changes and severity of gastrointestinal symptoms, including nausea, vomiting, flatulence, abdominal pain and decreased appetite (according to the diary data) in the treatment group as compared to the placebo group;
- Change in body weight at Visit 3 compared with Visit 1 in the placebo group as compared to the treatment group;
- Hospitalization rate in the treatment group compared with the placebo group;
- The number of days of using standard symptomatic therapy (as “rescue medication”) to relieve symptoms of acute diarrhea in the treatment group as compared to the placebo group;
- The number of patients using standard symptomatic therapy (as “rescue medication”) to relieve symptoms of acute diarrhea in the treatment group as compared to the placebo group.

### 5.1.2 Safety parameters

Safety evaluation will be based on the following parameters (between Visits 1 and 3), compared between the investigational medicinal product and placebo:

Frequency of adverse events (AEs) and/or serious adverse events (SAEs) in the treatment groups, including:

- Overall AE rate as compared to placebo;
- Frequency of AEs according to the results of physical examinations during each visit compared with placebo;
- AE incidence according to the results of the vital signs assessment (HR, BP, BT, RR) at each visit compared with placebo;
- AE incidence according to the ECG results on Day 15 ( $\pm 2$ ) compared with placebo;
- AEs incidence according to the results of laboratory examinations on Days 7( $\pm 2$ ) and 15( $\pm 2$ ) compared with placebo;
- Frequency of AEs according to the everyday patients’ records of well-being self-evaluation in the diary.

Diary records will be reviewed by the Investigator. In case the researcher considers that the records in the diary meet criteria of AE, the patient will be questioned about this event, and all information (including an evaluation of causality) will be documented.

Adverse event will be described according to the following scheme:

- Description of adverse event;
- Seriousness of adverse event (compliance with seriousness criteria);
- severity;
- duration;
- causal relationship with the investigational product;
- actions taken in relation to the study drug;
- actions taken in relation to the patient;
- outcome.

[figure not shown]
Adverse events will be coded according to MedDRA terms.

## 5.2 Description of study design

### 5.2.1 Study type

A multi-center, double-blind, randomized, placebo-controlled, parallel-group clinical study in two parallel groups.

### 5.2.2 Flowchart of study design

## 5.2.3 Study procedures

### 5.2.3.1 Schedule of research procedures in tabular form

**Table 6.** Visit schedule

| Study period   | Screening/
randomization/
start of
treatment | Treatment |            | Unscheduled
visits |
|--|---|-----------|------------|-----------------------|
|  |   | Visit 1   | Visit 2    |                       |
| Visits   | Visit 1   | Visit 2   | Visit 3    |                       |
| Day after starting therapy   | Day 1   | Day 7 ± 2 | Day 15 ± 2 |                       |
| Study procedures  |   |           |            |                       |
| Signing the Informed Consent Form                                  | •   |           |            |                       |
| Demographic data (date of birth, sex, age)                         | •   |           |            |                       |
| Body weight measurements   | •   | •         | •          |                       |
| Height measurement   | •   |           |            |                       |
| Medical history  | •   |           |            |                       |
| Complaints collection, medical history update                      | •   | •         | •          | •                     |
| Reporting concomitant treatment                                    | •   | •         | •          | •                     |
| Physical examination   | •   | •         | •          | •                     |
| Vital signs assessment                                 | •   | •         | •          | •                     |
| Complete blood count                                   | •   | •         | •          |                       |
| Blood chemistry profile                                | •   | •         | •          |                       |
| Urine pregnancy test                                   | •   |           |            |                       |
| Rapid test for the qualitative detection of immunoglobulin G (IgG) | •   |           |            |                       |

 SAD (mmHg), DAD (mmHg), respiratory rate (per minute), heart rate (beats per minute), axillary body temperature (°C)

 hemoglobin content, red blood cells, white blood cells, leukogram, ESR) will be carried out in the laboratory of the study site

 total protein, ALT, AST, total bilirubin

 only for women with preserved reproductive potential

| Study period  | Screening/
randomization/
start of
treatment | Treatment |            | Unscheduled
visits |
|---|---|-----------|------------|-----------------------|
|   |   | Visit 2   | Visit 3    |                       |
| Visits  | Visit 1   | Visit 2   | Visit 3    |                       |
| Day after starting therapy                          | Day 1   | Day 7 ± 2 | Day 15 ± 2 |                       |
| Study procedures                             |   |           |            |                       |
| and immunoglobulin M (IgM) antibodies to COVID-19   |   |           |            |                       |
| A 12-lead electrocardiogram                         | •   |           | •          | •                     |
| Evaluation of the inclusion/non-inclusion criteria  | •   |           |            |                       |
| Randomization                                | •   |           |            |                       |
| Dispensing of the investigational medicinal product | •   |           |            |                       |
| Dispensing of patient diary and thermometer         | •   |           |            |                       |
| Dispensing a laboratory stool collection kit        | •   | •         |            |                       |
| Collection of unused medication                     |   |           | •          |                       |
| Collection of patient diary                         |   |           | •          |                       |
| Collection of unused lab kits                       |   |           | •          |                       |
| Assessment of adverse events                        | •   | •         | •          | •                     |
| Evaluation of exclusion criteria                    |   | •         | •          | •                     |
| Assessment of the adherence to study                |   | •         | •          | •                     |

| Study period   | Screening/
randomization/
start of
treatment | Treatment |            | Unscheduled
visits |
|--|---|-----------|------------|-----------------------|
|  |   | Visit 2   | Visit 3    |                       |
| Visits   | Visit 1   | Visit 2   | Visit 3    |                       |
| Day after starting therapy   | Day 1   | Day 7 ± 2 | Day 15 ± 2 |                       |
| Study procedures  |   |           |            |                       |
| procedures (compliance with diary completion and study treatment)  |   |           |            |                       |
| Assessment of diarrhea, if documented in the diary and face-to-face interview regarding its classification as AAD (according to investigator's judgment) |   | •         | •          | •                     |

**5.2.3.2 Description of study procedures**

*5.2.3.2.1. Collection of medical history, demographic data, anthropometry*

When compiling medical history, it is necessary to pay attention to past diseases, concomitant chronic diseases, hereditary background, habitual intoxications (smoking status, alcohol consumption, drug addiction), allergic history, previous operations and injuries, occupational history, and constant or periodic medicinal therapy. In relation to this disease: the date and time of the onset of the first symptoms, the diagnostic and therapeutic measures carried out at the time of the examination, their effectiveness. The data about contraception method used by the male/female patient should be clarified; upon signing the informed consent, the male/female patient agrees to use one of the methods of contraception recommended in accordance with the study protocol throughout the study and a month after the completion of the study.

The primary documentation indicates gender, age of the patient, race and ethnicity of the patient. Patient's height is measured in centimeters using a height meter, and body weight in kilograms – using balance.

Height measurement should be performed for all patients (the reasons that make it impossible to measure height include hairstyle features (e.g., mohawk), the patient's refusal to take off his

headress for various reasons, - for example, a turban, the patient's inability to stand, and exceedence of height meter scale). Height is determined with the help of a height meter - a vertically placed board with divisions by centimeters and a horizontal ruler sliding on it. Scale error according to the standard should not exceed two millimeters. The patient is asked to remove shoes, heavy clothes, hairpins, and hair ornaments. The patient should touch the vertical board with the back of the head, back, buttocks, calves and heels; feet together. The upper border of the external auditory meatus should be on the same horizontal level with the lower border of the orbit (zygomatic bone). The patient is asked to look straight ahead. If the height of patient above the one of the researchers, the latter stands on the platform. The ruler of height meter must touch the head, then the divisions are counted. Reading of height meter should be taken while the patient is still under the ruler. The error should not exceed half a centimeter.

Patients should be weighed in the morning on an empty stomach, after urination and stool, in underwear (followed by a subtraction of the average clothes weight from a readout). The balance must stand on a rigid base, horizontally. The measurement error according to standards should not exceed 0.5 kg. Patient stands strictly in the center of balance with both feet. It is not allowed to record the body weight based on patient's words even in cases where weight measurement is not possible.

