### **3.5 Description and justification of the method of administration, dosage, dosing regimen and course of treatment**

#### **3.5.1 Description and justification of the method of administration, dosage, dosage regimen and course of treatment with the investigational drug**

To achieve a positive effect, probiotics should be taken in sufficiently high doses. The proposed dose of *Lactobacillus rhamnosus* GG is within the range of doses that have proven effective in well-planned and conducted randomized controlled trials described in the metanalysis Szajewska, 2015, Hempel, 2012, McFarland, 2006, as well as in the studies, carried out by Vanderhoof, 1999, Arvola, 1999, Johnston, 2006, Goldenberg, 2015. Besides, a dose of *Lactobacillus rhamnosus* GG in LRG-002 product corresponds to the doses recommended in the published guidelines of the World Gastroenterological Organization (WGO, 2017) and the European Society of Pediatric Gastroenterologists, Hepatologists and Nutritionists (ESPGHAN, 2016).

According to the recommendations of the World Gastroenterological Organization, given in the international guidelines on probiotics and prebiotics (WGO, 2017) considering dosage in the case of antibiotic-induced diarrhea, the recommended dose of *Lactobacillus rhamnosus* GG for children is  $1-2 \times 10^{10}$  CFU, and for adults  $10^{10}$  CFU twice daily.

The developed product contains at least  $10^{10}$  CFU of *Lactobacillus rhamnosus* GG per capsule.

The investigational medicinal product and placebo in the frameworks of this study in accordance with the draft instructions for medical use of LRG-002 medicinal product will be prescribed according to the following scheme:

Single dose - 1 capsule; the investigational medicinal product/placebo will be taken orally 2 times a day (morning and evening) for 14 days. The tested product / placebo capsule is swallowed with some water. In case Visit 1 took place in the afternoon, only one capsule is allowed on the first day.

The medicinal product is recommended to be taken with meals, as this ensures its maximum efficacy, not less than 3 hours after taking antibiotics.

It must not be taken concomitantly with alcohol, fruit juices or hot beverages.

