#### *5.2.4.1 Screening/randomization/treatment initiation (Visit 1)*

Visit 1 is carried out on Day 1. At this visit, the physician evaluates the patient's compliance with the criteria for participation in the study on the same day. If non-inclusion criteria are not identified, randomization is performed, the patient is given the investigational medicinal product/reference product, containers for collecting stool samples with the appropriate instructions, the patient's diary, and training is carried out to fill out the patient's diary (Appendix 3).

Procedures at Visit 1:

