#### **Visit 1 (Day 1)**

- Collection of demographic data (year of birth, sex, age);
- Body weight and height measurements;

- Medical history;
- Reporting concomitant treatment (including medications, food supplements and medical devices);
- Complaints reporting, medical history update;
- Physical examination;
- Measurement of vital signs (BP, HR, RR, BT);
- Complete blood count;
- Blood chemistry profile;
- Rapid test for the qualitative detection of immunoglobulin G (IgG) and immunoglobulin M (IgM) antibodies to COVID-19;
- Urine pregnancy test;
- A 12-lead electrocardiogram;
- The assessment of inclusion/non-selection criteria;
- Randomization;
- Dispensing of the investigational medicinal product (IMP)/placebo;
- Dispensing of patient diary and relevant training;
- Dispensing of a laboratory kit with the necessary consumables for collecting stool samples;
- Adverse event assessment.

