#### **5.2.4.3 Treatment completion visit (Visit 3, Day 15 ± 2)**

Visit 3 is carried out in the morning on the day 15 ± 2, the patient must come to the study site on an empty stomach, bring a completed diary and an unused product.

- Complaints reporting, medical history update;
- Body weight measurements;
- Reporting concomitant medications;
- Physical examination;
- Vital signs assessment;
- Adverse event recording;
- Evaluation of exclusion criteria;
- Assessment of the adherence to study procedures (compliance with diary completion and study treatment);
- Complete blood count;
- Blood chemistry profile;
- A 12-lead electrocardiogram;
- Diarrhea assessment based on patient diary entries and face-to-face interviews for classification as AAD as assessed by medical doctor (in the absence of results of stool analysis at the time of the visit, the assessment is carried out after the investigator receives the results from the laboratory);
- Collection of unused medication;
- Collection of unused containers for stool samples;
- Collection of patient diary.

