#### **5.5 Dosage regimen of the study medicinal products**

**Investigational medicinal product** LRG-002 is used according to the following dosage regimen: a single dose is 1 capsule for oral administration during meals with a small amount of water; the medicinal product will be taken orally 2 times a day for 14 days.

Placebo is used according to the following dosage regimen: a single dose is 1 capsule for oral administration during meals with a small amount of water; the medicinal product will be taken orally 2 times a day for 14 days.

If treatment order is received in the afternoon, the protocol allows only one capsule to be taken on the first day. The interval between taking the oral antibiotic and investigational medicinal product should be at least 3 hours in both groups.

Dosing regimen of investigational medicinal products:

| Day No. | Date       | Dosage frequency of LRG-002 product or placebo | Intake of antibiotic |
|---------|------------|--|----------------------|
| 1       | __/__/____ | 1 or 2   | Yes                  |
| 2       | __/__/____ | 2  | Yes                  |
| 3       | __/__/____ | 2  | Yes                  |
| 4       | __/__/____ | 2  | Yes                  |
| 5       | __/__/____ | 2  | Yes                  |
| 6       | __/__/____ | 2  | Yes                  |
| 7       | __/__/____ | 2  | Yes                  |
| 8       | __/__/____ | 2  | No                   |
| 9       | __/__/____ | 2  | No                   |
| 10      | __/__/____ | 2  | No                   |
| 11      | __/__/____ | 2  | No                   |
| 12      | __/__/____ | 2  | No                   |
| 13      | __/__/____ | 2  | No                   |
| 14      | __/__/____ | 2  | No                   |

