- A number of days of using symptomatic therapy to relieve symptoms of acute diarrhea in the treatment group as compared to the placebo group.

Due to the obvious difference between the distribution of these indicators from the normal (they have a discrete distribution), the nonparametric Mann–Whitney–Wilcoxon test implemented in the `wilcox.test` function will be used for intergroup comparison.

3. Other secondary endpoints:

- Weight change at Visit 3 compared with Visit 1 in the placebo group as compared to the treatment group. This BKT can have a distribution close to normal. Accordingly, at the first stage, the normality of the distribution will be assessed (using the Shapiro–Wilk test implemented in the shapiro.test function), at the second stage, either the t-test (t.test function) or the Mann–Whitney–Wilcoxon test (wilcox.test function) will be used.
- Stool consistency change (according to Bristol Stool Scale) (according to the diary) in the treatment group as compared to the placebo group; any individual changes in stool consistency will be classified as improved/unchanged/worsened, and the difference between the groups will be analyzed using chi-square criterion (chisq.test function).

8. Safety analysis

Safety parameters will be evaluated at every planned or unscheduled visit.

The safety assessment will be based on the following indicators (between Visits 1 and 3) compared between the investigational medicinal product and placebo:

- Changes in the vital signs over time and the incidence of pathological abnormalities revealed during the physical examination will be summarized by the group; a comparison will be made between the groups using appropriate tests for quantitative and qualitative data.

The data will be checked for compliance with the normal distribution law using the Shapiro–Wilk test.

Intergroup comparison of secondary endpoints related to quantitative scales will be performed using Student's t-test for independent samples if the data correspond to the normal distribution law; otherwise, the Mann–Whitney U test will be applied to independent samples.

Intergroup comparisons of secondary endpoints related to categorical scales will be performed using Pearson's chi-square test if the number of points in each cell of the crosstab is ≥ 5 , or Fisher's exact test if at least one of the crosstab cells contains < 5 points.

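### Weights should be taken fasted in the morning, but Visit 1 may fall in the afternoon while Visit 3 is a fasted morning visit, so weight change can mix weighing conditions with true change

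*Protocol*

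**What the plan says.** Protocol 5.2.3.2.1 gives the only rule on how to weigh: "Patients should be weighed in the morning on an empty stomach, after urination and stool". It adds a tolerance: "The measurement error according to standards should not exceed 0.5 kg".

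The Visit 1 list under Protocol 5.2.4.1 includes "Body weight and height measurements" and gives no time of day and no fasting state. The Visit 1 list in SAP 2.2.3 gives none either. On timing, Protocol 3.5.1 says: "In case Visit 1 took place in the afternoon, only one capsule is allowed on the first day". Screening cannot be spread over several days. Protocol 5.2.4.1 says: "At this visit, the physician evaluates the patient's compliance with the criteria for participation in the study on the same day", and Protocol 12.2 requires consent before any study procedure.

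For the last visit, Protocol 5.2.4.3 says: "Visit 3 is carried out in the morning on the day 15 ± 2, the patient must come to the study site on an empty stomach". SAP 2.2.3 keeps the fasting condition for Visit 3 but does not mention the morning.

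The endpoint, in Protocol 5.1.1.2 and 8.1 and in group 3 of SAP 7.2, is "Weight change at Visit 3 compared with Visit 1 in the placebo group as compared to the treatment group". SAP 7.2 checks normality with the Shapiro–Wilk test and then applies a t-test or a Mann–Whitney–Wilcoxon test to the change, with no covariate. Protocol 10.1.3 and SAP 7.2 treat all secondary efficacy analysis as exploratory, with no multiplicity correction and no power calculation.

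**The concern.** A change score is interpretable only if both weights are taken under like conditions. Here the final weight is taken under a fixed condition and the baseline need not be. If a patient is first weighed in the afternoon after eating and drinking, and last weighed fasted in the morning, part of the difference is a difference in weighing conditions. If afternoon weights are higher, the error always has the same sign and looks like weight loss.

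Two things are at stake. Mean change within each arm could be pulled down and misread when shown by arm. The comparison between arms would carry extra noise. The listed visit procedures do not provide for recording the time of weighing or fasting status, so neither effect could be examined afterwards.

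**Working it through.** **Plan's own figure.** The documents give no expected weight change, SD or sample size for this endpoint. The only sample size concerns the primary AAD endpoint: ((1.960 + 0.842)/0.11)² × (0.15×0.85 + 0.26×0.74) = 207.5, rounded up to 208 per arm. It reproduces, and this point does not affect it.

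**Can the rule be met at Visit 1?**
1. The rule requires a morning, fasted weight (Protocol 5.2.3.2.1).
2. The baseline weight is a Visit 1 procedure, and Visit 1 is Day 1 (5.2.4.1).
3. No study weight can be taken before consent (12.2), and eligibility and randomisation fall on that same day (5.2.4.1).
4. Visit 1 may take place in the afternoon (3.5.1).
5. So in a patient with an afternoon Visit 1 the baseline weight cannot follow the rule, and the text provides no other study weight to stand in for it.

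A morning Visit 1 can meet the rule, but nothing in the Visit 1 text asks the patient to arrive fasted. The food rules that touch Visit 1 are four hours before blood sampling (5.2.3.2.3) and two hours before vital signs (5.2.3.2.2). Neither is an overnight fast.

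**Illustration of size.** Every input here is an assumption, and none is in the documents:
- d, excess of an afternoon weight over the same patient's fasted morning weight: 0.5 to 1.5 kg
- q, share of Visits 1 held in the afternoon: 30% to 50%
- s, SD of true change over about two weeks: 1.0 to 1.5 kg

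Take d as constant, and afternoon attendance as unrelated to true change. Then:
- shift in mean change within each arm = -d × q
- variance ratio = 1 + d² × q × (1 - q) / s²
- information lost = 1 - 1/ratio

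| Case | d (kg) | q | s (kg) | Shift (kg) | Variance ratio | Information lost |
|---|---|---|---|---|---|---|
| Low | 0.5 | 0.3 | 1.5 | -0.15 | 1 + 0.0525/2.25 = 1.02 | 2% |
| Middle | 1.0 | 0.5 | 1.0 | -0.50 | 1 + 0.25/1 = 1.25 | 20% |
| High | 1.5 | 0.5 | 1.0 | -0.75 | 1 + 0.5625/1 = 1.56 | 36% |

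**Between arms.** The expected artefact is the same in both arms, so its expected difference is zero. The chance difference has standard error d × √(2q(1 - q)/n). With n = 208 per arm the middle case gives 1.0 × √(0.5/208) = 0.05 kg.

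**The case against.** Much of the case on the other side stands.

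- **Where an afternoon Visit 1 is stated.** A reader might infer that the synopsis, Protocol 5.5 and SAP 2.2 also place Visit 1 in the afternoon. They do not. Protocol 5.5 says: "If treatment order is received in the afternoon, the protocol allows only one capsule to be taken on the first day". The synopsis speaks of an appointment received and SAP 2.2 of a prescription received. A morning weighing followed by an afternoon order fits all three. Only Protocol 3.5.1 speaks of an afternoon Visit 1.
- **Competing rules.** A reader might infer that the protocol holds two weighing rules. It holds one. The difficulty is that the rule is not feasible at some Visits 1.
- **Bias.** A reader might infer that the treatment comparison is biased. The Visit 1 list puts weighing before randomisation, and allocation is blinded, so the shift is expected equally in both arms and cancels.
- **Importance.** The endpoint is exploratory and unpowered, and SAP 7.2 names no within-arm test of weight. A placebo arm showing the same shift would warn a careful reader. However, Table No. 3 in SAP Appendix 1 is a layout for within-group visit comparisons of quantitative variables, so within-arm change may well be presented.
- **Size.** All inputs are assumed, and the range runs from negligible to large. The four-hour rule limits the recent-meal part of the effect. Weighing error also belongs in the denominator. If it is uniform within ±0.5 kg (an assumption), two weighings add 2 × 1/12 = 0.167 kg², and the middle-case inflation falls from 25% to 0.25/1.167 = 21%.

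The adjustment for baseline differences in Protocol 10.1.1 and SAP section 5 does not answer the point. It is triggered by differences between arms, whereas this is a difference between visits.

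**Conclusion.** The point holds as a minor one. For patients whose Visit 1 is in the afternoon, the baseline weight cannot follow the protocol's own rule, and the planned change score then mixes weighing conditions that the plan neither adjusts for nor provides to record. The consequences are a likely downward shift in mean change within each arm and added variance. On the assumed inputs above the shift is -0.15 to -0.75 kg and the added variance 2% to 56%. The documents cannot narrow this, because they give neither the share of afternoon visits nor any variability for weight. The downward direction rests on the assumption that afternoon weights exceed fasted morning weights. The documents support no claim of a biased treatment comparison, and the primary AAD analysis and its sample size are untouched.

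**What to change.** 1. Reconcile Protocol 3.5.1, 5.2.3.2.1, the Visit 1 list under 5.2.4.1, and 5.2.4.3, so that the text says under what conditions the Visit 1 weight is taken when that visit is in the afternoon.
2. Add clock time and fasted yes/no to the eCRF with each weight. This has to be captured at weighing, since it cannot be reliably reconstructed later.
3. In SAP 7.2, keep the planned test and pre-specify beside it a linear model for weight change with treatment, age stratum and Visit 1 weighing condition (fasted morning, yes/no). The condition is fixed before randomisation, so adjusting for it is safe and removes the variance that it explains.
4. Keep all patients as the main summary. Report within-arm change among patients with a fasted-morning Visit 1 weight as a sensitivity analysis only.

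The cost is two eCRF fields and one additional model, with no extra visit. The sensitivity summary will rest on a subset of patients.
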